
(1) Age \geq 18 years and able to and demonstrate English reading literacy of at least 8th-grade level (REALM-R \geq 6)
 
(2) Postnatal women diagnosed or receiving treatment for depression with a severity-based entry criterion of moderate to severe (EPDS \geq 12)
 
(3) Willing to participate and able to give written informed consent
 
(4) Own a smartphone with a data plan
 
(5) Have a Facebook account and Facebook Messaging app on phone (or be willing to create account/download app during enrollment)
 
(6) Sufficient cognitive ability to provide self-report data on a computer touchscreen/ standard computer with minimal assistance
	
(1) Subjects with documented dysthymia or Axis II diagnoses.
 
(2) Subjects with self-reported or documented history of:
 
• anorexia or bulimia• obsessive compulsive disorder• prior hospitalization for suicidal ideation 
(3) Active suicidality as determined by clinician[†]
 
(4) Non-English speakers
 
.

[†] Suicidality may be incidentally disclosed during screening or identified via Question #10 of the EPDS ("The thought of harming myself has occurred to me:") An answer to Question #10 of "hardly ever", "sometimes", or "yes quite often", will trigger an evaluation for active suicidality by the clinician as described in Section VI (below).

Study-Wide Number of Subjects

Phase 1- Conducted at Univ. of Chicago only: 20 provider subjects and 5 patient subjects for a total enrollment of approximately 30 subjects.

Phase 2- 20 provider subjects and 40 patient subjects from each study site for a total enrollment of approximately 60 subjects per site (120 subject total).

Recruitment Methods

University of Chicago Medical Center – A social worker unaffiliated with the study will notify the research coordinator of any potential study participants for screening. We will recruit outpatients and inpatients.

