Phase 1 (Completed): We begin with a feasibility study in which all subjects receive CB-MBC care for 3 weeks. We will review the results and make any necessary changes in the chatbot platform before proceeding with the Phase 2 clinical trial. In Phase 2, subjects are randomized to Group 1 (usual care) or Group 2 (CB-MBC) and followed for 12 weeks, which is the outer-limit of the acute phase of depression recovery.³⁶ The primary outcome measure is depressive symptom severity. Exploratory secondary outcomes include side effect burden, patient-engagement, patient satisfaction, and provider satisfaction.

Interventions

Phase 1 (Completed) - All subjects will be asked to connect with the chatbot via Facebook Messenger. Subjects will then receive a 10-minute in person orientation to the chatbot and will be told to expect weekly messages from the chatbot asking them to complete a depression severity and side effect burden assessments. After one week, they will receive a check-in call from a study coordinator to answer any questions regarding use of the chatbot. Providers will receive weekly reports summarizing patient-level responses on administered assessments and are encouraged to respond if clinically-indicated. Upon completion of the study, the subject will be asked to participate in a semi-structured debrief interview focused on the user's experience.

Phase 2 - This is an open-label randomized control trial comparing depression severity in subjects entering treatment for major depression. Using a random number generator (www.random.org) subjects will be separated into the following groups:

Group 1: Subjects in this group will receive a monthly phone call reminding them to complete surveys that were securely emailed. The five (5) monthly surveys will ask about mood,

medication adherence if any, side effects from any medication, maternal functioning, and maternal confidence. The surveys could take up to 20 minutes to complete. The survey answers are stored in a secure database. Information collected will not be shared with the obstetric provider.

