Both groups: Upon completion of the study, subjects from both groups will be asked to participate in a semi-structured interview.

Survey Instruments

The following survey instruments will be utilized during the study. The schedule and survey administration method is described in Section 8 below.

Computerized Adaptive Testing: Depression Screen (CAT-DI): (secondary outcome), is a computerized adaptive dimensional severity measure for depression.³⁸ The CAT-DI utilizes a bank of about 375 depression items whose response patterns are fitted to a multidimensional item response theory model. Adaptive tests are then constructed that use the item parameters to select an optimal small subset of items from the item bank that is tailored to the subject’s depression severity, which is dynamically estimated as the subject responds to successive test items. The process continues until the uncertainty in this severity score estimate drops below a

pre-specified level (e.g., 5 points on a 100-point scale). A prior study has shown that an average of 12 items and a median time of 137 seconds had a 95% correlation of with a 389 total item bank score.³⁸ The resulting severity score maintains a strong correlation with the DSM-IV (SCID) diagnostic categories of none, minor depression (including dysthymia), and MDD. The CAT-DI categorized responses as 1) normal, 2) mild, 3) moderate, or 4) severe depression. The CAT-DI will be administered on a weekly basis via the chatbot interface to Phase 1 and Phase 2 (for Group 2 subjects). Severity results from the CAT-DI will form the basis of feedback provided to subjects in this arm. A refined version of the CAT-DI, optimized for perinatal depression, will be used for this study.³⁹

Rapid Estimate of Adult Literacy in Medicine, Revised (REALM-R)³⁵ is a word recognition test used to identify people at risk for poor health literacy. 11-items, administration time: 3 minutes This survey is administered on paper.

Edinburgh Postnatal Depression Scale (EPDS)⁴⁰ provides a discrete measure of perinatal depression. It will be administered by the research coordinator upon entry and then monthly via the chatbot, 10-item, administration time: 5 minutes. At screening this survey is administered on paper. At all following visits, subjects complete the survey via RedCap.

Medication Adherence Question will be used to document medication adherence, 1-item, administration time: 1 minute Subjects complete the survey via RedCap.

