The Frequency, Intensity, and Burden of Side Effects Rating (FIBSER)⁴¹ questionnaire uses 3 questions on a 6-point Likert measurement scale to measure 3 side effect domains of impact: frequency, intensity, and burden, administration time: 2 minutes Group 1 subjects complete the survey via RedCap. Group 2 subjects complete the survey via RedCap on some days and complete it using the chatbot interface on other days.

Confidence Questionnaire – to measure behavioral self-efficacy, 7-items, administration time: 5-minutes. This questionnaire has been previously used by our colleagues at NorthShore but not published. Subjects complete the survey via RedCap.

Barkin Index of Maternal Functioning⁴³ questionnaire designed to measure maternal functioning after childbirth, 20-items, administration time: 7 minutes Subjects complete the survey via RedCap.

A Debrief Tool has been developed to be used as the basis for semi-structured interviews following the trial, administration time: 6 minutes The study team will administer this interview over the phone or in person.

Study Activity Schedule

Table 1: Patient Timeline of Assessments – Phase 1 (Completed)

Timeline: Phase 1 – CB-MBC	Week 1		Week 2		Week 3	
	Days since enrollment					
	1	3	5	8	10	12

Screening: REALM-R & EPDS via interview											
Orientation training (10 minutes)											
Weekly notification to complete CAT-DI & FIBSER via CB-MBC											
User experience check-in phone call											
Debrief Interview											
Compensation (\$25)											

Table 2: Patient Timeline of Assessments for Groups 1 & 2 – Phase 2

Timeline: Phase 2 - Group 1: Usual Care (UC)	Month 1			Month 2			Month 3						
	Week												
	Screen	1	2	3	4	5	6	7	8	9	10	11	12
Screening: REALM-R & EPDS via interview	X												
Randomize		X											
Reminder phone call from RA		X			X				X				X
EPDS, FIBSER, BIMF, CQ & Medication Adherence via RedCap		X			X				X				X
Debrief Interview													X
Compensation (\$25)					X				X				X
Timeline: Phase 2 – Group 2: CB-MBC	Month 1			Month 2			Month 3						
	Week												
	Screen	1	2	3	4	5	6	7	8	9	10	11	12
Screening: REALM-R & EPDS	X												
Randomize		X											
Orientation training (10 minutes)		X											
User experience check-in phone call		X											
Reminder phone call from RA to complete questionnaires		X	X	X	X	X	X	X	X	X	X	X	X
EPDS, FIBSER, BIMF, CQ & Medication Adherence via RedCap		X			X				X				X
CAT-DI & FIBSER via CB-MBC		X	X	X	X	X	X	X	X	X	X	X	X

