Risk of additional/reduced assessment or treatment. Treating providers will not have access to screening or follow-up depression severity and side effect information obtained from monthly telephone interviews. Assessment results from subjects randomized to CB-MBC will be automatically sent to the provider on a weekly basis. It is a desired outcome that these assessment results motivate the provider to consider contacting the subject and possibly modifying their treatment plan. This type of additional assessment and treatment would be expected to be beneficial goal of this intervention. We believe the risk of an adverse event related to additional assessment by the provider to be minimal.

Conversely, participation in the study will not prohibit involvement in any other type of assessment and/or treatment. All participants will be allowed (and/or encouraged) to participate in whatever type or amount of treatment is thought to be clinically indicated for the subject. Thus, participation in the study will not cause any participant to be deprived of a clinically appropriate assessment and/or treatment.

Risk of disclosure of suicidal ideation. Women with perinatal depression are at higher risk for experiencing suicidal ideation. We will be actively assessing for suicidal ideation via in-clinic screening and telephone assessments. There is also the risk of inadvertent disclosure of self-harm behavior during these contact points. In addition, for patients using the chatbot, the CAT-DI depression item bank includes 11 items that make reference to death, suicide, or self-harm. Thus, there is a risk of increased detection of suicidality or self-harm during the study. Safety procedures will be described in the section below.

Risk of other serious adverse events. The overall potential for serious adverse events leading to physical or psychological harm during the study is minimal as we are testing an information technology intervention. Risk of increased suicidal or self-harm behaviors. We are unaware of any literature to suggest that the act of tracking depression symptoms in depressed patients increases the risk of suicide or worsening depression as compared to usual care. The principal

investigator will report the adverse event to the IRB within 48 hours.

Risk of social harm. There is minimal risk of social harm to the subject.

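### The plan says suicidal ideation is actively assessed by telephone, but the Phase 2 schedule contains no telephone assessment, so in usual care detection by the study rests on one emailed item that may go unanswered

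*Combined protocol and SAP*

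**What the plan says.** **Where telephone assessment is described.** The Risks section, on disclosure of suicidal ideation, says: "We will be actively assessing for suicidal ideation via in-clinic screening and telephone assessments". The Risks paragraph on additional or reduced assessment treats follow-up severity data as coming from monthly telephone interviews. Protections Against Risk (physical harm) also mentions phone interviews. Its bullet on detection during telephone follow-up sets out what to do if ideation emerges while an EPDS is being given.

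**What Phase 2 schedules.** Interventions, Group 1: "Subjects in this group will receive a monthly phone call reminding them to complete surveys that were securely emailed". The Phase 2 patient timeline (the second table numbered 2) puts the reminder call and the REDCap EPDS on separate rows, both at weeks 1, 4, 8 and 12. Group 2 has "Reminder phone call from RA to complete questionnaires" in every week, plus one check-in call about using the chatbot. Survey Instruments says of the EPDS after screening: "At all following visits, subjects complete the survey via RedCap". The same entry also says: "It will be administered by the research coordinator upon entry and then monthly via the chatbot". Neither mode is the telephone.

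**Other protections.** Exclusions include "Active suicidality as determined by clinician" and "prior hospitalization for suicidal ideation". Any non-zero item 10 at screening leads to a clinician evaluation. On REDCap, a score of 1 to 3 on item 10 opens a safety branch and sends an alert. Chatbot users also complete the CAT-DI weekly, with its own safety response.

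**The concern.** Women enter with an EPDS of 12 or more, and the protocol itself says that women with perinatal depression are at raised risk of suicidal ideation. The entry exclusions lower the starting risk but do not address ideation that appears during the 12 weeks.

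For that period the plan gives two accounts. In the risk and safety text, staff ask about ideation by telephone. In the schedule, staff telephone only to prompt an online form, and the woman's own answer is what sets off the safety response. Staff working from the schedule would not ask. A reader of the Risks section would believe that they do.

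The difference matters most in usual care. Group 2 has the weekly CAT-DI as well as the EPDS. Group 1 has the emailed EPDS alone.

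**Working it through.** The plan states no figure on this point. The check sets the schedule against the safety text and counts from the Phase 2 patient timeline.

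**1. Scheduled calls after screening, leaving the week-12 debrief aside**
- Group 1: weeks 1, 4, 8, 12 = 4.
- Group 2: 12 weekly reminders + 1 check-in = 13.
- None has a described self-harm question. The debrief may be by telephone; its content is not shown and no self-harm question is described for it.

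**2. Scheduled occasions for a self-harm question after screening**
- Group 1: EPDS at weeks 1, 4, 8, 12 = 4.
- Group 2: 4 EPDS + 12 CAT-DI = up to 16. It is "up to" in effect only, because the CAT-DI is adaptive and its self-harm items are not certain to be presented.

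**3. Longest interval between answered self-harm questions, Group 1**

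| Surveys returned | Calculation | Weeks |
|---|---|---|
| All | max(4−1, 8−4, 12−8) | 4 |
| All but week 4 | 8−1 | 7 |
| All but week 8 | 12−4 | 8 |
| Week 1 only | 12−1, to end of follow-up | 11 |

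If week 1 is the one missed, the interval runs from screening to week 4. The time from screening to week 1 is not stated, so no figure is given.

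**4. With item 10 asked by telephone when the EPDS is outstanding.** If the woman is reached at every call, the longest interval is max(3, 4, 4) = 4 weeks in every row.

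**5. Illustration of how often this could arise.** The documents give no survey non-return rate. As a stand-in, take the 5% wave-to-wave attrition from the power calculation, and assume 1:1 allocation of the 2 × 40 = 80 Phase 2 patients (the ratio is not stated) with nobody missing at week 1. Expected missing EPDS at wave k = 0 to 3 is 40 × (1 − 0.95^k) = 0, 2.0, 3.9, 5.7. That sums to 11.6 of 40 × 4 = 160 occasions. At an assumed 10% the sum is 22.4, and at an assumed 20% it is 41.9. Attrition is not the same as non-return, and some of these women could not be reached by telephone either. The point does not depend on these figures.

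**6. Do the other protections fill the gap?**
- The exclusions and the screening evaluation act at entry.
- The distress rule and the telephone pathway, as scheduled, depend on what the woman shows or volunteers.
- The monthly data review could reveal a missing survey, but no action on one is specified.
- Reminder calls, and payments at weeks 4, 8 and 12, may reduce non-return. They do not ask the question.

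**The case against.** **A telephone assessment may be intended and simply left out of the schedule.** The telephone bullet under Protections Against Risk is separate from the REDCap bullet and expressly covers an EPDS. A reader might infer from the schedule that nobody will ever ask about self-harm by telephone; the documents do not settle that. What stands is that the plan contradicts itself, and on either reading some text must change.

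**The question is scheduled.** A reader might infer that a woman who does not return her survey has no scheduled self-harm question at that time point. That is not so. Item 10 is sent to her at weeks 1, 4, 8 and 12 and goes unanswered. By the schedule her longest interval after week 1 is 4 weeks whatever she does. The 7, 8 and 11 weeks are intervals between answers.

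**Care continues outside the study.** A reader might infer that her ideation would go undetected altogether. Eligible women are already diagnosed with or treated for depression, participation does not restrict other assessment or treatment, and the protocol says all receive standard care. Her own clinicians may ask. The supportable claim is that the study may not detect it.

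**Adding a question is a choice.** Correcting the text alone would remove the contradiction. That is true, and it is offered below as the minimum. It would leave the dependence on an answered survey as it is.

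**Conclusion.** The point holds, at the level of something the sponsor should correct. The Risks and Protections text describes telephone assessment of suicidal ideation, and the Phase 2 schedule does not contain it. In usual care, item 10 of the emailed EPDS is the only described self-harm question after screening, and the alert depends on its being answered. When a survey is not returned, the study may not detect new ideation unless the woman discloses it or is visibly distressed.

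The size is 4 weeks between answers with full return, rising to 7, 8 or 11 weeks in the patterns of non-return shown. This rests on reading the timeline literally and on the debrief containing no self-harm question. The number of women affected cannot be estimated from the documents.

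Confidence is high on the contradiction. It is lower on what callers would do in practice, since a telephone assessment may have been meant.

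**What to change.** 1. Email the survey a fixed number of days before each scheduled call at weeks 1, 4, 8 and 12. The sponsor chooses the number; the plan gives none. Alternatively, state that week 1 is left to the recent in-clinic screening.
2. In both arms, if the REDCap EPDS is still outstanding at that call, the caller reminds the woman and then asks item 10 only. The answer is recorded as safety data outside the EPDS total. Any score of 1 to 3 enters the existing telephone pathway.
3. If she is not reached, record that item 10 was not asked. Flag any EPDS completed after item 10 was asked by telephone. Report both by arm.
4. Align Survey Instruments, Risks, Protections Against Risk and the Phase 2 patient timeline on REDCap as the EPDS mode, with this fallback. Suggested wording for Risks: *After screening, suicidal ideation is assessed by item 10 of the REDCap EPDS. If the EPDS is outstanding at the week 1, 4, 8 or 12 call, the caller asks item 10. Group 2 also completes the CAT-DI.* (Drop week 1 if it is left to screening.)
5. At the least, if no fallback is adopted, remove the statement that ideation is actively assessed by telephone.

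**Cost.** Protocol wording, a fixed send date, brief caller training, and a minute or two (assumed) on calls already scheduled.

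**Downsides.** Women who cannot be reached stay unasked, probably including many who have stopped responding, so the 11-week case may gain least. Some women will meet item 10 twice. Item 10 counts towards the EPDS total, which is the primary outcome. Being asked it by telephone, or the clinical contact that a positive answer triggers, may slightly influence the later self-completed form, and this could differ by arm if non-return does. The flag in step 3 makes that visible.
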